1.0 TRIAL DESIGN

1.1 Trial Design

This is a phase II, single-center, single-arm trial to evaluate the efficacy and safety of pembrolizumab in post-remission treatment of patients ≥ 60 years with AML who are not candidates for HCT. Patients must have achieved CR or CRi with induction chemotherapy and have an ECOG performance status of 0-1. Patients can receive no consolidation or up to 4 cycles of consolidation per treating physicians' preference. Patients are eligible if their last dose of chemotherapy was received within 3 months of trial enrollment. Remaining in CR or CRi is required prior to enrollment. The enrollment target for this study is 40 patients evaluable for efficacy. Planned analysis will occur 18 months after the initiation of treatment of the last patient on the trial.

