7.0 STATISTICAL ANALYSIS PLAN

7.1 Analysis Samples

For both the primary safety and efficacy endpoints, the analysis sample will be eligible patients who have taken at least one dose of pembrolizumab. Patients who are eligible but withdraw prior to taking the first dose will not be included in these analyses and will be replaced, so that, barring early stopping, the analysis sample will be 40 patients who have taken at least one dose of drug.

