7.2 Statistical Analysis Plan Summary

7.2.1 Primary Efficacy Objective: *To evaluate the time to relapse (TTR) in patients > 60 years with AML in complete remission undergoing post-remission therapy with pembrolizumab.* The time to relapse function will be estimated by the product-limit (Kaplan-Meier) method, with an appropriate 80% confidence interval. Death is considered a censoring event in determining TTR.

The median TTR will also be estimated, along with an appropriate confidence interval. Assuming an exponential time to failure distribution, 26% two-year TTR under the standard induction therapy is associated with a median of 12.3 months. The null hypothesis that the treatment with pembrolizumab offers no increase in TTR will be tested by determining if 12.3 months is within an 80% confidence interval around the median, a one-sided $\alpha=0.10$ test. The sensitivity of the treatment of death as a censoring event will be assessed by repeating the above analysis on relapse-free survival, where death and relapse are both considered events. Patients who drop out of the study will be treated as censored at the last observation time.

Potential prognostic factors for TTR in this population will also be explored. These include the use of consolidation therapy (0 vs 1-4), cytogenetic risk category (high-risk, intermediate risk, or low risk), FLT3 status (FLT3-ITD mutation present or absent), NPM1 status (NPM1 mutation present or absent), age >70 years, minimal residual disease, and ECOG performance status. The survival distributions for TTR will be computed using the Kaplan-Meier method and the log-rank test used to test for statistical differences in the distributions for the aforementioned exposure groups. Multivariate analysis using Cox regression will then be used to adjust for all significant covariates. Patients who drop out of the study will be treated as censored at the last observation time. Patients with missing covariate data will be excluded from this exploratory analysis.

7.2.2 Primary Safety Objective: *To evaluate the safety and tolerability of pembrolizumab in patients > 60 years with AML.* The NCI CTCAE type and grade of adverse events and their association with treatment will be tabulated. Section 8.3 contains a stopping rule for excess toxicity.

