7.4 Justification of Design

The plot presents the power of the hypothesis test of the primary efficacy endpoint against the median TTR after *pembrolizumab* treatment. It is seen that 80% power is achieved (at $\alpha=0.1$ in a one-sided test) if the true median TTR is 19.5 months or greater. The stopping rule is based on a beta-binomial probability model that stops the trial if $PP(P(\text{Toxicity}) > 0.2) > 0.8$, where PP is the posterior probability function for $P(\text{Toxicity})$. The posterior model includes a binomial data model and a Beta(2,8) prior for the $P(\text{Toxicity})$. The plot displays the operating characteristics of the rule as a function of the true (unobserved) probability of toxicity. It is seen that, for instance, if the true probability of toxicity is 0.4, the probability the trial will stop early is 0.5, and the expected number of patients accrued is 28.

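### Exploratory prognostic Cox model (7.2.1): letting log-rank significance choose among seven factors, with no stated alpha and about 20–32 relapses, risks spurious factors and tends to inflate modest effects

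*Combined protocol and SAP*

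**What the plan says.** Section 7.2.1 plans, after the primary analysis, to explore prognostic factors for TTR. The list begins "These include the use of consolidation therapy (0 vs 1-4), cytogenetic risk category (high-risk, intermediate risk, or low risk), FLT3 status" and goes on to NPM1 status, age over 70, minimal residual disease (MRD) and ECOG status. That makes seven factors, or 8 degrees of freedom with cytogenetics at three levels.

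The procedure has two steps. Kaplan-Meier curves are drawn by factor, with "the log-rank test used to test for statistical differences in the distributions for the aforementioned exposure groups". Then: "Multivariate analysis using Cox regression will then be used to adjust for all significant covariates". The section gives no significance level for this step, no multiplicity control and no limit on model size. It does not ask for HRs for factors that are not retained. Patients lacking covariate values are dropped. The section calls the work exploratory.

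On sample size, 7.1 says that, barring early stopping, "the analysis sample will be 40 patients who have taken at least one dose of drug".

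**The concern.** The same 40 patients choose the covariates and then estimate their effects. With few relapses, a factor passes the gate only if its observed effect is large. Two consequences follow: a factor with no effect can enter by chance, and a modest real effect is seen mainly in the samples that exaggerate it. The final Cox output carries no sign of either.

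The missing alpha adds to this. The only level given in 7.2.1 is the one-sided 0.10 of the primary test, so a reader cannot tell whether the gate is 0.05 or 0.10, and the two give quite different error rates. At stake is how far a later reader can trust the reported prognostic factors and their HRs.

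**Working it through.** **Inputs from the documents.** N = 40 (7.1). The null median rests on "26% two-year TTR under the standard induction therapy is associated with a median of 12.3 months" (7.2.1). The design alternative is reached "if the true median TTR is 19.5 months or greater" (7.4). Accrual takes 18–24 months (Trial Summary). "Planned analysis will occur 18 months after the initiation of treatment of the last patient on the trial" (1.1), so follow-up at analysis runs from 18 months to 36–42 months. "Death is considered a censoring event in determining TTR" (7.2.1), so deaths without relapse lower the relapse count.

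**Assumptions.** The documents do not give these: a gate of two-sided 0.05, with 0.10 as the other case; factor prevalences of 15–50%; non-relapse death or dropout of 0 to 0.01 per month; uniform accrual.

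**The plan's own figure.** 24 × ln 2 / (−ln 0.26) = 16.64 / 1.347 = 12.35 months, against 12.3 stated. The plan states no event count, alpha or power for the prognostic analysis, so there is nothing further of its own to reproduce here.

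**Step 1: relapses.** With hazard λ = ln 2 / median and accrual A, the expected count is 40 × [1 − (e^(−18λ) − e^(−(18+A)λ)) / (Aλ)].

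- Median 12.3, A = 24: λ = 0.0564; 40 × [1 − (0.363 − 0.094) / 1.352] = 32.0. With A = 18: 30.9.
- Median 19.5, A = 24: λ = 0.0355; 40 × [1 − (0.527 − 0.225) / 0.853] = 25.8. With A = 18: 24.4.
- Adding death or dropout at 0.01 per month gives 28.0–28.8 and 21.8–22.9.
- Also stopping follow-up at 24 months gives 26.5–26.7 and 20.2–20.4. The Trial Summary lists two years of participation, although 6.1.5.4 allows follow-up to five years.

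The range is therefore about 20–32, before any loss from missing covariates.

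**Step 2: chance of a spurious factor when none is prognostic.** If the tests were independent, the chance is 1 − 0.95^7 = 30.2% at 0.05 and 1 − 0.90^7 = 52.2% at 0.10. Simulating the seven log-rank tests at N = 40 gives about 32–35% and 54–56%. Nesting NPM1 within FLT3, as eligibility implies, leaves it at 33% (at 0.05). When one to three of the seven are truly prognostic, the chance that a null factor is also kept is 22–31%.

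**Step 3: effect size needed to pass.** For a 50:50 factor the standard error of log HR is about s = 2/√E, so the observed HR must exceed exp(1.96 × 2/√E). That is 2.00 at 32 relapses, 2.16 at 26 and 2.40 at 20.

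**Step 4: size of retained effects.** Let a = 1.96 − ln(HR)/s. Ignoring rare wrong-direction selections, the chance of being kept is 1 − Φ(a), and the mean log HR when kept is ln(HR) + s·φ(a)/(1 − Φ(a)). For E = 26, s = 0.392:

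- HR 1.5: a = 0.926; kept 18%; mean log HR 0.405 + 0.392 × 0.260/0.177 = 0.98, so HR about 2.7 (2.63 with wrong-direction selections counted).
- HR 2.0: a = 0.193; kept 42%; mean log HR 0.693 + 0.392 × 0.392/0.424 = 1.055, so HR 2.87.

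At 32 relapses the corresponding values are 2.42 and 2.65. Simulation at N = 40 runs slightly higher for a balanced factor: about 2.5–2.7 for a true 1.5 and 2.8–3.1 for a true 2.0.

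Refitting the multivariable Cox model on the selected factors (24–32 relapses, unequal prevalences) gives:

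| True HR | Median reported HR | Share of kept estimates too high |
|---|---|---|
| 1.5 | 2.6–2.7 | 93–94% |
| 2.0 | 2.6–3.0 | 89–97% |
| 3.0 | 3.3–3.4 | 61–65% |
| 4.0 | 4.0–4.2 | 50–55% |

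**The case against.** The strongest reply is that the plan calls this analysis exploratory, and that it feeds neither the primary test, which rests on the confidence interval for the median, nor the toxicity stopping rule. That stands, and it limits the weight of the point. It does not say what level the gate uses, and it does not correct the HRs that the gate produces.

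Several stronger readings are tempting, and the documents do not support them:

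- **Every retained effect is overstated.** Inflation is a tendency for modest effects. At a true HR of 4, retained estimates are about as often too low as too high.
- **A false factor appears a third of the time.** That needs all seven factors to be null and a 0.05 gate, which is an assumption.
- **Intervals are generally too narrow.** After selection, nominal 95% intervals covered a true HR of 1.5 about 85–88% of the time, but coverage was about 94–95% at HR 2.
- **Factors not retained are reported as having no effect.** No such rule is written, and Kaplan-Meier curves by factor are planned. What is missing is any request for their HRs.
- **A confounder left out would bias the treatment result.** The trial has one arm, so the model adjusts no treatment contrast.

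There is also a fair objection to any fixed model: the choice of factors is a judgement. MRD is an awkward choice because the dedicated assay is sent only where feasible (5.1, footnote e) and incomplete cases are dropped.

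**Conclusion.** The point holds as a weakness of the exploratory prognostic analysis. With about 20–32 relapses and no stated alpha, the gate has about a 32–35% chance of keeping at least one spurious factor if none is prognostic (two-sided 0.05 assumed; about 54–56% at 0.10). It tends to report a true HR of 1.5 at about 2.5–2.7 and one of 2.0 at about 2.8–3.1 for a balanced factor, with little inflation from HR 3 upward. These figures rest on exponential TTR at the design medians and on the assumed prevalences, and the upper relapse count assumes no death or dropout. A reader might infer that the trial's efficacy conclusion is compromised. It is not: the primary TTR test does not use this model. This is a cheap improvement to how prognostic findings are produced and reported.

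**What to change.** In 7.2.1:

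1. Report the unadjusted HR with 95% CI for all seven factors, whether or not significant.
2. Describe the log-rank p-values as descriptive and the prognostic results as hypothesis-generating.
3. Replace entry by significance with one Cox model of about two or three parameters, named by the sponsor before the analysis. Three parameters give about 7–11 relapses each (20/3 to 32/3), against 2.5–4 for all eight (20/8 to 32/8).
4. Choose factors expected to be complete and adequately filled under the eligibility rules. MRD may be incomplete. Low-risk cytogenetics is largely excluded by 4.1.3 (item 3), and the same item makes NPM1 overlap with FLT3. Under 4.1.1, patients with fewer than two consolidation cycles enter only if judged intolerant, so the no-consolidation group may be small.
5. Section 7.2.3 says the overall survival analysis resembles that of TTR. State whether this includes the prognostic step and, if so, apply the same wording.

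The cost is SAP wording, with no extra patients, visits or data. The sponsor gives up a data-driven final model and must choose the adjustment factors in advance.

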| 9.3 | Compliance with Trial Registration and Results Posting Requirements | 52 |

| | | |
|------|--|-----|
| 9.4 | Quality Management System..... | 52 |
| 9.5 | Data Management..... | 52 |
| 10.0 | LIST OF REFERENCES..... | 543 |
| 11.0 | APPENDICES..... | 58 |
| 11.1 | ECOG Performance Status..... | 58 |
| 11.2 | Common Terminology Criteria for Adverse Events V4.0 (CTCAE)..... | 58 |

TRIAL SUMMARY

[figure not shown]
| | |
|---------------------------------------|---|
| Title | A Phase II study of Pembrolizumab as Post-remission Treatment of Patients ≥ 60 with AML Who Are Not Transplantation Candidates |
| Short Title | Pembrolizumab as Maintenance Therapy for AML in CR1 |
| Protocol Number | |
| Phase | Phase II |
| Methodology | Open label |
| Study Center(s) | Single-center |
| Primary Objective | To evaluate the time to relapse (TTR) in patients > 60 years with AML in complete remission undergoing post-remission therapy with pembrolizumab. |
| Number of Subjects | 40 subjects |
| Diagnosis and Main Inclusion Criteria | Patients with AML in first complete remission/complete remission with incomplete count recovery who are not unable or unwilling to undergo allogeneic stem cell transplant or who allogeneic stem cell transplant is not indicated. |
| Study Product, Dose, Route, Regimen | Pembrolizumab, intravenous, 200mg, every 3 weeks with dosing adjustments as needed for toxicity |
| Duration of administration | Total duration of pembrolizumab is up to 2 years if patients tolerate the therapy and remain in complete remission |
| Reference therapy | Patients who achieve a complete response to induction chemotherapy followed by chemotherapy consolidation therapy who do not undergo allogeneic transplant are observed. Despite the high relapse rates in this group, there is not therapy that has been proven to be effective to prevent relapse. |
| Statistical Methodology | The relapse function will be estimated by using the Kaplan-Meier method. A 26% two-year TTR under the standard induction therapy is associated with a median of 12.3 months. The null hypothesis that the treatment with pembrolizumab offers no increase in TTR will be tested by determining if 12.3 months is within an 80% confidence interval around the median, a one-sided $\alpha=0.10$ test. |
| Estimated Enrollment Period | 18-24 months |
| Estimated duration of trial | 4 years, but with planned analysis at 18 months after last patient enrolled |

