2.2 Secondary Objective(s) & Hypothesis(es)

- (1) **Objective:** To evaluate overall survival with post-remission pembrolizumab treatment in patients > 60 years with AML

Hypothesis: Post-remission treatment with pembrolizumab will improve overall survival compared to historical controls (where the median OS is 17.2 months) in patients \geq 60 years with AML who are not candidates for HCT.

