3.2 Rationale

3.2.1 Rationale for the Trial and Selected Subject Population

Acute myeloid leukemia (AML) is a malignant hematopoietic disorder characterized by the unregulated growth of myeloid precursors (blasts) and associated marked reduction in normal hematopoiesis. It is the most common acute leukemia in adults, with an estimated 18,860 new cases of AML diagnosed per year in the United State and 10,460 deaths. [23] Disease related morbidity and mortality arise from cytopenias, leading to complications such as bleeding and/or infection, as well as end organ damage from the circulating blasts. If left untreated, AML can lead to death within weeks. [24]

The standard treatment for newly diagnosed AML consists primarily of an anthracycline combined with a nucleoside analogue, cytarabine. The goal of remission induction chemotherapy is the rapid restoration of normal bone marrow function. [25] Once a complete remission is attained, relapse invariably occurs without additional consolidation therapy. Consolidation approaches are based on prognosis and age, but may include 1-4 cycles of high dose cytarabine chemotherapy or allogeneic stem cell transplant. While consolidation therapy reduces relapse, up to 50% of younger patients still relapse. [26]

Although standard therapeutic approaches are tailored to younger patients, the median age of diagnosis of acute myelogenous leukemia (AML) is 67 years. [27] Unfortunately, the outcomes for patients older than 60 years are quite poor. Population studies in AML report 5-year survival rates of 3% to 8% compared to up to 50% for younger patients. [28] Intensive induction therapy, as described above, remains the standard of care for those elderly patients who are able to tolerate it, but rates of complete remission (CR) range from 20% to 60% dependent on the number of adverse prognostic conditions present. [29] The 2-year DFS of patients ≥ 60 yrs of age with AML who undergo induction therapy has been consistently at 24-26% in two large studies conducted in 2001 and 2010. [30; 31] Unfortunately, there have been no important advances in induction therapy since then.

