4.0 METHODOLOGY

4.1 Entry Criteria

4.1.1 Diagnosis/Condition for Entry into the Trial

Subject eligible for entry into the trial must have a diagnosis of non-M3 AML and currently be in first CR/CRi (see Appendix I for response criteria). Patients should receive 2-4 cycles of consolidation, provided that the last dose of either induction chemotherapy or consolidation chemotherapy falls within 3 months prior to enrollment in this trial. A patient receiving less than 2 of consolidation therapy is eligible only if they are deemed intolerant to consolidation therapy by the treating physician.

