7.2.3 Secondary Efficacy Objective: *To evaluate overall survival with post-remission pembrolizumab treatment in patients \geq 60 years with AML.* The analysis plan is similar to that of TTR. Assuming an 8% five-year survival rate with induction therapy alone, median overall survival is 17.2 months.

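### The 17.2-month overall survival benchmark does not follow from the stated 8% five-year survival (the plan's own exponential conversion gives 16.5 months), and the 8% is apparently not a remission-cohort rate.

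*Combined protocol and SAP*

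**What the plan says.** Section 7.2.3 sets the benchmark for overall survival (OS) in one sentence: "Assuming an 8% five-year survival rate with induction therapy alone, median overall survival is 17.2 months". It cites no source for the 8% and names no distribution. On method it says only: "The analysis plan is similar to that of TTR".

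Section 2.2 carries the figure into the hypothesis of improved survival against historical controls: "where the median OS is 17.2 months".

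The TTR plan in 7.2.1 does state its model: "Assuming an exponential time to failure distribution, 26% two-year TTR under the standard induction therapy is associated with a median of 12.3 months". It then tests whether 12.3 months lies inside an 80% confidence interval around the observed median, one-sided at 0.10.

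The only other five-year figure of 8% is in the rationale, 3.2.1, as the upper end of a range for older patients: "Population studies in AML report 5-year survival rates of 3% to 8" per cent. Section 1.1 requires trial patients to be in CR or CRi with ECOG 0-1.

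**The concern.** The sentence in 7.2.3 presents 17.2 months as a consequence of 8% at five years. If the two disagree, one of them is wrong or an unstated model was used, and a reader cannot tell which. Because 2.2 names 17.2 months as the control median, it is the figure against which the trial's survival result will be read.

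A second question is whether the 8% describes patients like those in the trial. A rate for older patients with AML in general includes people who never reach remission. A difference from such a benchmark, in either direction, could reflect who was enrolled rather than what the drug did.

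Only a secondary endpoint is at stake. The primary TTR test and the sample size do not use this number.

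**Working it through.** **Inputs.** 26% at 24 months, median 12.3 months, exponential (7.2.1). 8% at 60 months, median 17.2 months (7.2.3; the median again in 2.2). Range 3% to 8% at five years (3.2.1).

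**Formula.** Under an exponential curve, median = t × ln 2 / (−ln S(t)).

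**Reproducing the plan's TTR figure.** 24 × 0.6931 / 1.3471 = 12.35 months (12.349 before rounding), which agrees with the stated 12.3. This is evidently the conversion the plan used.

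**The same conversion for OS.** 60 × 0.6931 / 2.5257 = 16.47 months, against the stated 17.2. The difference is 0.73 months, or 4.3% of 17.2.

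**Could rounding explain it?**
- 7.5% gives 16.06 months and 8.5% gives 16.87. Any rate that rounds to 8% therefore gives 16.1 to 16.9.
- In reverse, 0.5^(60/17.2) = 0.0891, so a 17.2-month median implies 8.9%. Medians of 17.15 to 17.25 imply 8.85% to 8.97%.
- A rate of 9% gives 17.27, which rounds to 17.3. It is closer than 8% but still not an exact match.
- 17.2 months would go with 8% at 62.7 months rather than 60.
- The full 3% to 8% range in 3.2.1 converts to 11.9 to 16.5 months, so 17.2 lies above all of it.

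**Could another convention explain it?** With 8% at 60 months:

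| Variant | Median (months) |
|---|---|
| Discrete monthly hazard | 16.82 |
| Discrete quarterly hazard | 17.53 |
| Discrete yearly hazard | 20.97 |
| Monthly hazard rounded to 0.04 | 17.33 |
| Monthly hazard rounded to 0.042 | 16.50 |
| 30-day months | 16.71 |
| 28-day months | 17.90 |

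None gives 17.2. A Weibull curve with shape ln(2.5257/0.6931) / ln(60/17.2) = 1.035 would pass through both stated OS points. No such curve is stated, and the same shape would give a TTR median of 24 × (0.6931/1.3471)^(1/1.035) = 12.6 months rather than 12.3.

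**Comparability.** No arithmetic settles this, so the texts are set side by side. Section 7.2.3 gives 8% without a source. Section 3.2.1 gives 3% to 8% from population studies of older patients, not limited to those in remission. Section 1.1 admits only patients in CR/CRi with ECOG 0-1. No start date for OS is given in the plan, and 7.2.3 does not say from when the 8% is counted, while 4.1.2 allows enrollment up to 3 months after the last chemotherapy.

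**The case against.** The best reply on the arithmetic is that 7.2.3 states no distribution for OS. Its reference to TTR describes the analysis plan and need not import the exponential assumption. Even if it does, the error may lie in the 8% rather than in the 17.2. That stands: the documents do not show which number is wrong, so a flat instruction to replace 17.2 by 16.5 would go too far. What remains is that the two figures disagree under the only model the plan states.

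It is also fair to say that the slip is small, does not favor the drug and leaves the primary analysis alone. That too stands.

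On comparability, linking the 8% to 3.2.1 is an inference, since 7.2.3 cites nothing. It is the only matching figure in the documents, but that supports moderate confidence at most.

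Three stronger readings are tempting and are not supported:

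- **The bar is too low, so an inactive drug would look effective.** A reader might divide the 8% by a remission rate to get a higher control median. But 3.2.1 gives its remission rates ("rates of complete remission (CR) range from 20% to 60" per cent) for patients who can tolerate intensive induction, which is not the group behind a population survival rate. Any result would also swing widely over that range. The exclusion of favorable-risk disease and of transplant candidates in 4.1.3 could pull the other way, as could the lower end of the 3% to 8% range.
- **The error rate of the OS test is distorted by a known amount.** Section 7.2.3 specifies no null hypothesis, level or interval method for OS beyond its similarity to TTR. A rejection rate would rest on an assumed test and assumed follow-up.
- **A control given induction only is being compared with consolidated patients.** Section 4.1.1 says "Patients should receive 2-4 cycles of consolidation", and the Trial Summary describes the reference group as "Patients who achieve a complete response to induction chemotherapy followed by chemotherapy consolidation therapy who do not undergo allogeneic transplant are observed". But 4.1.1 also admits patients intolerant of consolidation with fewer than 2 cycles, 1.1 allows none to 4, and 7.2.1 compares 0 with 1-4. Section 7.2.1 uses a similar induction label for the TTR control, so the wording in 7.2.3 may simply mean treatment without pembrolizumab.

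**Conclusion.** The arithmetic point holds with high confidence: 8% at five years and a 17.2-month median are inconsistent under the exponential conversion that reproduces the plan's TTR benchmark. The gap is 0.7 months (16.5 against 17.2), or equivalently 8% against about 8.9%. If the 8% is right, the stated bar is slightly too hard to beat, so the error is mildly conservative. The conclusion assumes that the exponential model was meant for OS as well; no other model is stated.

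The comparability point holds with moderate confidence. The benchmark appears to come from a population not restricted to patients in remission with good performance status, and its time origin is not stated. The documents do not determine the direction or the size of any bias. It follows that neither 17.2 nor 16.5 is shown to be a like-for-like control median; it does not follow that the benchmark is too low.

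**What to change.** - Reconcile the rate and the median in 2.2 and 7.2.3. If 8% and the exponential model are kept, the median is 16.5 months. Otherwise correct the rate or state the model that yields 17.2.
- Cite the source of the five-year rate.
- Define the start date for OS.
- Either replace the benchmark with a cited one for older, non-transplant patients in first remission with a matching start date, or label the present one as not like-for-like and present the OS comparison with it as descriptive (Kaplan-Meier curve and median with its confidence interval). Word the hypothesis in 2.2 to match.

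The cost is a wording change in two sections. The descriptive option means a more modest secondary claim; the replacement option means finding a suitable published cohort. The primary TTR test, the sample size and the trial procedures do not change.
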